8.4.3 REPORTING UNANTICIPATED PROBLEMS TO PARTICIPANTS

Any new information gained during the study that may affect a participant’s willingness to continue in the study will be reported to all currently enrolled participant.

9. STATISTICAL CONSIDERATIONS

Statistical analyses will be performed by [name].

9.1 STATISTICAL HYPOTHESES

- Primary Outcome hypothesis:
 - Null: There is no difference in goal-directed behavior between baseline S-EEfRT and S-EEfRT during stimulation to dlPFC as a function of stimulation type (delta-beta TMS, theta-gamma TMS, or arrhythmic).
 - Alternate: There is a difference in goal-directed behavior between baseline S-EEfRT and S-EEfRT during stimulation to dlPFC as a function of stimulation type (delta-beta tACS, theta-gamma tACS, or active-sham).
- Secondary Outcome hypothesis:
 - Null: There is no difference in delta-beta phase-amplitude coupling strength between prefrontal electrodes and left motor electrodes for the decision period of the S-EEfRT as a function of stimulation type to dlPFC (delta-beta TMS, theta-gamma TMS, or arrhythmic TMS).
 - Alternate: There is a difference in delta-beta phase-amplitude coupling strength between prefrontal electrodes and left motor electrodes the decision period of the S-EEfRT as a function of stimulation type to dlPFC (delta-beta TMS, theta-gamma TMS, or arrhythmic TMS).
- Exploratory Outcome hypothesis 1:
 - Null: The impact of delta-beta TMS to dlPFC on goal-directed behavior is not correlated with personality traits related to motivation.
 - Alternative: The impact of delta-beta TMS to dlPFC on goal-directed behavior is correlated with personality traits related to motivation.
- Exploratory Outcome hypothesis 2:
 - Null: There is no difference in reward-evaluation between baseline S-EEfRT and S-EEfRT during stimulation to mPFC as a function of stimulation type (delta-beta TMS, theta-gamma TMS, or arrhythmic).
 - Alternate: There is a difference in reward-evaluation behavior between baseline S-EEfRT and S-EEfRT during stimulation to mPFC as a function of stimulation type (delta-beta tACS, theta-gamma tACS, or active-sham).
- Exploratory Outcome hypothesis 3:
 - Null: There is no difference in theta-gamma phase-amplitude coupling strength between prefrontal electrodes and posterior parietal electrodes for the decision period of the S-EEfRT as a function of stimulation type to mPFC (delta-beta TMS, theta-gamma TMS, or arrhythmic TMS).
 - Alternate: There is a difference in theta-gamma phase-amplitude coupling strength between prefrontal electrodes and posterior parietal electrodes the decision period of the S-EEfRT as a function of stimulation type to mPFCs (delta-beta TMS, theta-gamma TMS, or arrhythmic TMS).
- Exploratory Outcome hypothesis 4:
 - Null: Functional connectivity during the S-EEfRT between dorsal striatum and lateral prefrontal cortex is not predictive of the impact of delta-beta TMS to dlPFC on goal-directed behavior.

- Alternative: Functional connectivity during the S-EEfRT between dorsal striatum and lateral prefrontal cortex is predictive of the impact of delta-beta TMS to dIPFC on goal-directed behavior.

9.2 SAMPLE SIZE DETERMINATION

The sample size is 24 participants in the final dataset to be used in analysis. However, to ensure that 24 participants complete the experiment, we conservatively estimate to enroll 50 participants as a ceiling for the sake of IRB approval. The motivation for the sample size of 24 participants in the analysis is explained below. The sample size is determined based on previous experiments from our group: the effect size of previous findings and the reliability of our estimates. Our estimators are precise due to sufficient number of trials per condition with each participant and that the tasks are titrated to the individual.

Primary outcome: Rhythmic TMS to lateral frontal cortex at delta-beta frequency will increase goal-directed behavior relative to arrhythmic TMS.

Previous Data: The planning and refinement of the proposed study was informed by our previous experiments that serve as preliminary data for the proposal. In our previous experiment, we delivered rhythmic TMS to lateral frontal cortex to increase performance in a cognitive control task (Riddle et al. 2020b). In our previous study, there was a significant interaction between TMS site and TMS frequency in a two-way repeated-measures ANOVA such that the improvement in performance in the cognitive control task was site and frequency-specific. The effect size from the partial-eta square was 0.23, and the effect from a dependent t-test was 0.532, with 20 participants. The experimental design of this previous study is similar to the current study in that there are two sites for stimulation (lateral frontal and medial frontal) with two different stimulation frequencies (delta-beta and theta-gamma). Both studies used an arrhythmic condition to control for non-specific effects of TMS.

Sample Size Determination and Power Calculation: Based on this previous effect size, we estimated that our participant count at 24 participants is powered at >95%.

[figure not shown]

Figure 3. Power calculation for the interaction effect in two-way repeated-measures ANOVA modeled as within factors interaction in a two-way ANOVA with partial-eta square of 0.23, and a correlation between variables of 0.77 based on Riddle, Scimeca et al. 2021. Power calculation run using the G*Power software. Proposed number of participants is 24 and is depicted in red.

Data will be collected until we reach 24 participants. Given the similarity with our previous experiment (Riddle, Scimeca, et al., 2020), we are confident that our current analysis will be sufficiently powered.

Secondary outcome: Rhythmic TMS to lateral frontal cortex at delta-beta frequency will increase frontal delta-beta coupling strength.

Previous Data: The planning and refinement of the proposed study was informed by our previous experiments. In our previous experiment, we delivered rhythmic TMS to lateral frontal cortex and found an increase in oscillatory power and an increase in phase entrainment specific to the targeted frequency band (Riddle, McPherson, et al.). In our previous experiment that delivered theta frequency TMS (4-8Hz) to lateral frontal cortex, we found an increase in oscillatory power in theta frequency (effect size of 0.540) and a robust increase in phase alignment across trials (effect size of 1.01). We use the phase alignment metric (inter-trial phase coherence) to estimate the required power to find a similar impact of delta-beta stimulation to align the phase of delta oscillations to task-modulated beta amplitude. The analysis of our previous experiment used 47 participants. Based on our previous effect size for entrainment, we would need 15 participants to reach 95% statistical power for this comparison. A more conservative estimate of a large effect size (0.60), we would need 24 participants to reach 80% statistical power.

[figure not shown]

Figure 4. Power calculation for increased phase alignment of delta oscillations to beta power from delta-beta TMS. The effect size estimate is based on phase entrainment in EEG from rhythmic TMS (larger effect, above). A more conservative effect size estimate would be to use the impact of rhythmic TMS on oscillatory amplitude (large effect, below). Both effect sizes were modeled as a dependent t-test using the G*Power software. The proposed number of participants is 24 and is depicted in red.

Data will be collected until we reach 24 participants. Given the similarity in methodology between the current experiment and our previous experiment (Riddle, McPherson, et al.), we are confident that we are sufficiently powered with 24 participants.

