9.4 STATISTICAL ANALYSES

9.4.1 GENERAL APPROACH

All testing described below assumes a significance threshold of $p = 0.05$. Analyses will be deemed to be statistically significant if the p -value is less than this threshold. An analysis that does not exceed this threshold will be considered inconclusive. Continuous data will be described using means, standard deviations, and confidence intervals, while categorical data will be described using counts/percentages.

There may be additional covariates included in the analysis. Data will be assessed for normality and, if deemed necessary, corrective procedures will be applied (e.g., log normalization). Based on our previous dataset, we expect that the variables used here will be approximately Gaussian. However, if the distribution of a variable displays a skewed tail and a test for normality fails, then it is justified to use a corrective procedure. This correction will be applied upon consideration of the variables themselves, and not based on the result of the intended analysis.

Data will be collected until 24 participants complete the study and all data is usable. Given that recruitment will be feasible in a convenience sample, we expect to have complete data and all analyses will include the full participant pool. However, if there are technical errors that are not caught in time, then the affected analyses may have less participants. In this scenario, the data for a participant is then completely removed from the analysis.

The effects of stimulation are expected to be transitory, lasting for only a second or two after stimulation. For this reason, stimulation is delivered “online” immediately preceding the time at which the cognitive processes of interest are engaged. During each session, we include a control condition (arrhythmic TMS) that will be subtracted from the conditions of interest (delta-beta TMS and theta-gamma TMS). Therefore, we control for any effects of sequence or time within each session by subtracting each metric of interest from the condition-matched arrhythmic TMS metric. Furthermore, any learning effects from performing the reward-based decision-making task should be stabilized by the 3rd session. These methods are typical

in cognitive neuroscience paradigms. For the reasons listed above, it is unlikely that there will be any effect of sequence or carryover effects between sessions.

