9.4.2 ANALYSIS OF THE PRIMARY OUTCOME (BEHAVIOR)

Goal-directed behavior will be calculated as the average decision to perform the HARD task. The average of the two blocks for each stimulation conditions will be calculated (three stimulation types by two stimulation sites). A two-way repeated-measures analysis of variance (ANOVA) will be performed using within-participant factor of stimulation type (delta-beta TMS versus theta-gamma TMS; each subtracted by session-matched arrhythmic TMS) and within-participant factor stimulation site (dIPFC TMS versus mPFC TMS). We control for the effect of time with a subtraction of delta-beta TMS versus arrhythmic TMS and theta-gamma TMS versus arrhythmic TMS. In other words, four values are submitted to the ANOVA for each participant.

1. Delta-beta TMS to dIPFC minus arrhythmic TMS to dIPFC
2. Theta-gamma TMS to dIPFC minus arrhythmic TMS to dIPFC
3. Delta-beta TMS to mPFC minus arrhythmic TMS to mPFC
4. Theta-gamma TMS to mPFC minus arrhythmic TMS to mPFC

Thus, only differences from our active control, arrhythmic TMS, are considered meaningfully worth interpretation. We hypothesize to find an interaction between stimulation site and stimulation type in the ANOVA. Post-hoc differences will be investigated using Tukey's method to address multiple comparisons. We hypothesize that the predicted interaction will be driven by an increase in goal-directed behavior for delta-beta TMS to dIPFC. Sensitivity analyses will be conducted to evaluate the specificity of these effects: a similar analysis with reward-evaluation as the dependent variable and we do not expect that delta-beta TMS will have any effect on reward-evaluation.

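### The stated power above 95% for the primary interaction at n = 24 does not follow from the plan's own effect size, which gives about 70%

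*Combined protocol and SAP*

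**What the plan says.** Section 9.2 plans the primary outcome on an earlier TMS study that found a site-by-frequency interaction: "The effect size from the partial-eta square was 0.23, and the effect from a dependent t-test was 0.532, with 20 participants". From this it concludes "we estimated that our participant count at 24 participants is powered at >95" percent. The Figure 3 caption gives the G*Power inputs as "partial-eta square of 0.23, and a correlation between variables of 0.77", and the primary-outcome text closes with "we are confident that our current analysis will be sufficiently powered".

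For the secondary outcome, the same section says: "A more conservative estimate of a large effect size (0.60), we would need 24 participants to reach 80% statistical power". It also says that the larger effect of 1.01 needs 15 participants for 95%. The Figure 4 caption adds: "Both effect sizes were modeled as a dependent t-test using the G*Power software".

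Section 9.4.2 defines the primary test as the interaction in a two-by-two within-participant ANOVA: "In other words, four values are submitted to the ANOVA for each participant". Section 9.4.1 sets the threshold at 0.05 and says of a non-significant result: "An analysis that does not exceed this threshold will be considered inconclusive".

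**The concern.** Two statements in Section 9.2 do not fit together. An effect of 0.60 is said to have 80% power with 24 participants, while an effect quoted as 0.532 is said to have more than 95% with the same 24. If both refer to a paired comparison, the smaller effect cannot have the higher power.

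This is the only power figure for the primary outcome. If it is too high, readers and the IRB are misinformed about how likely this four-session stimulation study is to end without a clear primary answer. The danger is not a false claim of no effect, because Section 9.4.1 treats a non-significant result as inconclusive. It is that the risk of an inconclusive result is presented as small when it is not.

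**Working it through.** **Inputs.** From Section 9.2: n = 24; earlier partial eta-squared 0.23; earlier dependent-t effect 0.532; earlier n = 20; correlation 0.77. From Section 9.4.1: alpha 0.05. Sidedness is not stated. The primary alternative in Section 9.1 is non-directional, and the secondary power figures reproduce only two-sided (step 3), so two-sided is used.

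**1. What the primary test is.** Write DB, TG and A for delta-beta, theta-gamma and arrhythmic stimulation. The interaction contrast for one participant is

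[(DB − A) − (TG − A)] at dlPFC − [(DB − A) − (TG − A)] at mPFC = (DB − TG) at dlPFC − (DB − TG) at mPFC.

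The arrhythmic term cancels within each site, leaving one number per participant. The interaction F-test on 1 and n − 1 degrees of freedom is the square of the one-sample t-test on that number. Its effect size is dz, the mean of the contrast divided by its standard deviation.

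**2. Are 0.23 and 0.532 the same effect?**

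- f² = 0.23 / 0.77 = 0.2987
- F(1,19) = 0.2987 × 19 = 5.68, so t = 2.38
- dz = 2.38 / √20 = 0.533

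In reverse, dz = 0.532 at n = 20 gives partial eta-squared 0.2295. The two figures agree to rounding.

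**3. Reproducing the secondary figures.** These use the noncentral t distribution with n − 1 degrees of freedom and noncentrality dz × √n.

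| Effect | n | Two-sided power | Smallest n, two-sided | Smallest n, one-sided |
|---|---|---|---|---|
| 0.60 | 24 | 80.4% | 24 for 80% | 19 for 80% |
| 1.01 | 15 | 95.3% | 15 for 95% | 13 for 95% |

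The plan's 24 and 15 match the two-sided column only.

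**4. The same method for the primary outcome.** With dz = 0.532 and n = 24, the noncentrality is 0.532 × √24 = 2.61.

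- Two-sided power: 70.4%. One-sided: 81.2%, still far from 95%.
- The F version with noncentrality f² × (n − 1) = 0.2987 × 23 = 6.87 gives 70.9%.
- A simulation of 100,000 two-by-two within-participant trials, with pairwise correlation 0.77 and interaction dz 0.533, gives 70.6%.
- For dz = 0.532, two-sided, 30 participants are needed for 80%, 40 for 90% and 48 for 95%.
- At n = 24, 80% power needs dz of about 0.60 and 95% needs about 0.77.

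**5. Reproducing the figure above 95%.** It is obtained if f² is put into the repeated-measures formula with noncentrality f² × n × m / (1 − ρ), where m is the number of measurements. The plan does not state m or the software's effect-size option, and Figure 3 is not available, so this route is inferred.

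| m | ρ | Noncentrality | Implied dz = √(noncentrality / 24) | Power (1 df) |
|---|---|---|---|---|
| 2 | 0.77 | 62.3 | 1.61 | > 99.99% |
| 4 | 0.77 | 124.7 | 2.28 | > 99.99% |
| 2 | 0 | 14.3 | 0.77 | 95.2% |
| 4 | 0 | 28.7 | 1.09 | 99.9% |

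A partial eta-squared observed in a within-participant analysis already reflects the correlation between conditions. Dividing by 1 − 0.77 counts it twice and turns an effect of 0.53 into 1.6 or more. Setting ρ to zero does not repair the figure, because the multiplication by m remains.

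**6. Precision of the planning effect.** With t = 2.38 on 19 degrees of freedom, the 95% interval for dz is 0.06 to 1.00. Over that range, power at n = 24 runs from 6% to above 99%.

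**The case against.** Four points can be made for the plan.

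- **The 80% figure belongs elsewhere.** It concerns a different outcome, a different earlier experiment (47 participants) and a directly modelled t-test. Section 9.2 does not say which comparison produced 0.532 or call it a dz. Identifying it with the interaction is therefore an inference, though the conversion in step 2 leaves little doubt. The result does not depend on it, because partial eta-squared 0.23 alone on a 1-df test leads to about 70%.
- **The stated inputs do return more than 95% under one software convention.** This is true. The fault lies in the choice of convention for that effect size rather than in the software's calculation, and the figure is still wrong for the planned test.
- **This is a pilot, and a non-significant result is already labelled inconclusive.** This limits the harm: no interpretation rule, dataset or participant is affected. But the plan makes a quantitative power claim and draws assurance from it, so the claim should be correct.
- **The earlier estimate is imprecise, so 70% is not firm either.** This stands, and the corrected text should say so. The plan bases its claim on that estimate, however, so the claim has to be judged there, and the imprecision gives no support to a figure above 95%. Comparing about 30% with under 5% is likewise conditional on that effect.

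**Conclusion.** The concern holds. At the plan's own planning effect, the primary interaction test has about 70% power with 24 participants, not more than 95%. The chance of a non-significant primary result is then about 30%, roughly six times the 5% ceiling that the plan implies. Rounding of 0.23 (0.225 to 0.235) moves the power only between 69% and 72%.

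This rests on a two-sided 0.05 test, complete data on 24 participants, and a true effect equal to the earlier estimate. That estimate comes from 20 people doing a different cognitive task. The explanation through the 0.77 correlation is inferred, and the finding does not need it. Whether 0.77 is a true correlation cannot be settled from the documents; it also equals 1 − 0.23. The secondary-outcome calculation is correct in itself and arrives at 24, but it does not support the primary claim.

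**What to change.** In Section 9.2, replace the primary power statement with wording such as: 24 participants give 80% power for a standardized interaction contrast (dz) of at least 0.60 at two-sided 0.05, and about 70% if the true effect equals the earlier estimate (dz 0.532, from 20 participants and therefore imprecise).

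Redo Figure 3 and its caption as a one-sample or paired t-test on the interaction contrast, matching the method of Figure 4. If an F-test calculation is preferred, use noncentrality f² × (n − 1), and state the software option chosen. Changing only the correlation input is not enough. Remove or qualify the closing assurance of sufficient power for the primary outcome.

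The cost is a few sentences, one figure and its caption, and a less favourable stated power. The sample size of 24, the design, the endpoint and the test need not change.

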9.4.3 ANALYSIS OF THE SECONDARY OUTCOME (ELECTROPHYSIOLOGY)

Delta-beta phase amplitude coupling will be calculated between the phase of delta oscillations (2-3 Hz) in prefrontal electrodes (FCz and surrounding electrodes) and the amplitude of beta oscillations (15- 25 Hz) in left motor electrodes (C3 and surrounding electrodes). The instantaneous phase and amplitude of these oscillations will be calculated by averaging the signal in these two regions of interest, band-filtering the signal to the specified range, and then performing the Hilbert transform on the signal. Phase-amplitude coupling (PAC) is then calculated by creating a hybrid signal using the amplitude of beta oscillations in left motor electrodes and the phase of delta oscillations in prefrontal electrodes:

$$PAC = \left| \frac{\sum_{t=1}^N M * e^{i\theta}}{N} \right|, M \text{ is magnitude of beta oscillations, } \theta \text{ is angle of delta oscillations, } N \text{ is number of time points}$$

The PAC value is normalized by creating a null distribution by randomly shifting the beta timeseries by at least 10% of the number of time points. Then, PAC is calculated between the delta-phase timeseries and each of these randomly shifted beta-amplitude timeseries. Finally, PAC_z is calculated as the z-transformed true PAC value relative to the null distribution.

The average during the decision epoch of each trial of the task during stimulation will be calculated. The average of the two blocks for each stimulation conditions will be calculated (three stimulation types by two stimulation sites). A two-way repeated-measures analysis of variance (ANOVA) will be performed using within-participant factor of stimulation type (delta-beta TMS versus theta-gamma TMS; each subtracted by session-matched arrhythmic TMS) and within-participant factor stimulation site (dIPFC TMS versus mPFC TMS). We control for the effect of time with a subtraction of delta-beta TMS versus arrhythmic TMS and theta-gamma TMS versus arrhythmic TMS. In other words, four values are submitted to the ANOVA for each participant.

1. Delta-beta TMS to dIPFC minus arrhythmic TMS to dIPFC
2. Theta-gamma TMS to dIPFC minus arrhythmic TMS to dIPFC
3. Delta-beta TMS to mPFC minus arrhythmic TMS to mPFC
4. Theta-gamma TMS to mPFC minus arrhythmic TMS to mPFC

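### Section 9.2's 15 participants for 95% power belongs to inter-trial phase coherence and is not shown to apply to the delta-beta coupling endpoint

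*Combined protocol and SAP*

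**What the plan says.** Section 9.2 (secondary outcome) reports from an earlier theta-TMS experiment with 47 participants an effect of 0.540 on oscillatory power and "a robust increase in phase alignment across trials (effect size of 1.01"). It then says: "We use the phase alignment metric (inter-trial phase coherence) to estimate the required power to find a similar impact of delta-beta stimulation". The sentence goes on to give the premise, namely that stimulation will align delta phase to beta amplitude that the task modulates. The conclusion is "Based on our previous effect size for entrainment, we would need 15 participants to reach 95% statistical power for this comparison".

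A fallback follows: an effect of 0.60 needs 24 participants for 80% power. The Figure 4 legend links this fallback to oscillatory amplitude and adds "Both effect sizes were modeled as a dependent t-test using the G*Power software". The subsection closes by expressing confidence that 24 participants are enough, citing the similarity of method to the earlier experiment.

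Section 9.4.3 defines the endpoint. PAC is the modulus of the mean, over time points, of beta magnitude at left motor electrodes times exp(i × delta phase at prefrontal electrodes). The beta series is then shifted at random by at least 10% of the time points to build a null distribution, and "PAC_z is calculated as the z-transformed true PAC value relative to the null distribution". On aggregation it says "The average during the decision epoch of each trial of the task during stimulation will be calculated", followed by averaging over the two blocks per condition. Arrhythmic values are subtracted, and the hypothesised result is a site-by-type interaction in a two-way repeated-measures ANOVA.

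**The concern.** Inter-trial phase coherence asks whether a single band has the same phase from one trial to the next. PACz asks whether beta amplitude follows delta phase over the time points of the decision epoch, relative to shifted data. An effect size for the first is not an effect size for the second. Section 9.2 gives no TMS effect on coupling, and nothing in the plan converts one metric into the other.

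What is at stake is how the secondary result will be understood. A reader of section 9.2 would take the coupling analysis to have power well above 95% with 24 participants (99.7% at 1.01), when that figure describes a variable the secondary analysis does not test.

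**Working it through.** **Inputs.** Effect sizes 1.01, 0.60 and 0.540; N of 15 and 24; paired t-test (section 9.2 and Figure 4 legend). Alpha: "All testing described below assumes a significance threshold of $p = 0.05" (section 9.4.1). Sidedness is not stated for the power calculation. Two-sided is inferred from the non-directional alternative in section 9.1, "There is a difference in delta-beta phase-amplitude coupling strength between prefrontal electrodes and left motor electrodes the decision period", and is the choice that reproduces both stated sample sizes.

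**Step 1: reproduce the plan.** For a paired t-test, power is the probability that a noncentral t variable with n − 1 degrees of freedom and noncentrality d × √n exceeds the two-sided 5% critical value in absolute size.
- d = 1.01, n = 15: noncentrality 1.01 × √15 = 3.91, power 95.3%. The stated figure reproduces.
- d = 0.60, n = 24: noncentrality 0.60 × √24 = 2.94, power 80.4%. The stated figure reproduces.
- One-sided testing would give 13 and 19 participants instead.

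The arithmetic is correct. The question is which variable it describes.

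**Step 2: does alignment across trials move PAC computed within a trial?** Let stimulation shift the delta phase of a trial by a constant c. Then |(1/N) Σ M·exp(i(θ + c))| = |exp(ic)| × |(1/N) Σ M·exp(iθ)| = |(1/N) Σ M·exp(iθ)|, because |exp(ic)| = 1. Each shifted surrogate is unchanged for the same reason, so per-trial PACz is unchanged too. This is exact for a constant phase reset.

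**Step 3: does it move PAC computed on pooled time points?** This was simulated. Assumptions: 60 trials (two blocks of 30, as planned), 2 s epochs sampled at 200 Hz, 2.5 Hz delta with slight phase drift, beta amplitude with a 30% delta-rate modulation locked to trial time plus noise, and 60 simulated data sets per setting.

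| Quantity | No alignment | Strong alignment |
|---|---|---|
| Inter-trial coherence | 0.111 | 0.795 |
| PAC per trial, mean | 0.145 | 0.146 |
| PACz per trial | −0.065 | −0.024 |
| PAC pooled, unnormalised | 0.016 | 0.119 |
| PACz pooled, one shift of the whole series | −0.083 | 0.214 |

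With beta not modulated, pooled unnormalised PAC did not respond (0.004 to 0.005). A second simulation of pooled PAC with task-locked beta compared surrogate schemes. PACz stayed near zero (−0.2 to 0.1) under one shift of the whole series, but rose from −0.3 to 8.2 when each trial was shifted independently. Section 9.4.3 is compatible with either scheme. These runs show direction only; the sizes depend on the assumed settings.

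**Step 4: what 24 participants can detect.** The planned interaction is one contrast per participant: value 1 minus value 2, less value 3 minus value 4, in the numbering of section 9.4.3. Its F test on 1 and 23 degrees of freedom is the square of a paired t statistic, so the Step 1 formula applies with dz defined on that contrast. With no coupling effect size in the documents, a range has to be assumed:

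| dz on the contrast | Power, n = 24 |
|---|---|
| 0.30 | 29% |
| 0.40 | 47% |
| 0.50 | 65% |
| 0.54 | 72% |
| 0.60 | 80% |
| 0.80 | 96% |
| 1.01 | 99.7% |

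The smallest detectable dz is 0.60 at 80% power and 0.77 at 95% power.

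**The case against.** The sponsor can make four fair replies.

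1. The proxy and its mechanism are stated openly. Beta modulated by the task is the section's own premise, so it is not an omitted assumption. This stands. But the premise comes without data on modulation at the delta rate and without a conversion to PACz, so disclosure does not make 95% a power figure for coupling.
2. A reader might infer from Step 2 that the endpoint cannot respond to alignment at all. The documents do not support that. Section 9.4.3 suggests per-trial computation but does not state it, and Step 3 shows a pooled version that responds.
3. A reader might go further and put power at the type I error rate, about 5–6%. A simulation in which the conditions differ only in phase concentration does return that for per-trial PAC, but only because it gives TMS no effect on coupling. The intervention delivers 20 Hz triplets at a 3 Hz rate (section 4.3) and could act on beta or on coupling directly.
4. The sample size does not rest on 15 participants. The planned 24 coincides with the 0.60 / 80% case, and this is a pilot. This also stands, and it limits the point to what is claimed. The fallback does not supply the missing effect size, however: it is tied to oscillatory amplitude, whose reported effect of 0.540 gives 71.7% power with 24.

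Nor do the documents support the inference that a null result would be reported as failed target engagement: section 9.4.1 says a non-significant analysis will be treated as inconclusive.

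**Conclusion.** The concern holds in limited form. The calculation behind 15 participants and 95% power is correct for inter-trial phase coherence with an effect of 1.01. It is not shown to apply to PACz, and the actual power for PACz is unknown: it could be low or high, depending on an effect size that the documents do not give. For assumed dz between 0.30 and 0.80 on the interaction contrast, power with 24 participants runs from 29% to 96%.

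This rests on two-sided testing at 0.05 and on the constant-reset algebra for the per-trial reading. For the pooled reading it rests on simulations that show only that the answer turns on details the plan leaves open. It is an error in the choice of input, affects a secondary outcome, and does not call the sample size or the endpoint into question.

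**What to change.** - In section 9.2 and the Figure 4 legend, state that 15 participants for 95% power refers to inter-trial phase coherence only, and withdraw it as a power statement for delta-beta coupling.
- State that no effect size for TMS on phase-amplitude coupling is available.
- Replace the expression of confidence in sufficient power with the detectable effect: with 24 participants and two-sided 0.05, dz of about 0.60 at 80% power, where dz is defined on the one-degree-of-freedom site-by-type interaction contrast of PACz.
- In section 9.4.3, state whether PAC and its surrogates are computed within each trial or on pooled time points and, if pooled, whether the shift is applied to the whole series or trial by trial.

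The cost is wording in two sections and one legend. The stated power becomes less favourable. Sample size, data collection and endpoint stay as they are.
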